**D. Describe any procedures that will be used for quality control of collected data.**

Qualtrics and Excel databases will be created in such a way as to not allow for out of range data.

**E. Describe how data will be handled study-wide:**

Data (described in Table 1) will only be accessed and handled by IRB approved study personnel and kept in password protected databases. [name] is ultimately responsible for the receipt and transmission of all data. Paper copies of data (e.g., names on consent forms) collected at the New Brunswick Housing Authority will be brought immediately to Rutgers offices where they will be locked in a cabinet housed behind a locked door (of Division of Addiction Psychiatry, [name]).

## **6.2 Data Security**

Our research team employs standard procedures to ensure confidential information about study participation is not disclosed. All data are linked to an arbitrary 3-digit study ID unrelated to personal information. The file linking participants to their study ID will be stored in a password-protected file, located within a password-protected database on an encrypted computer. Only select trained laboratory personnel will have access to the file. All computer files or printed data used for analysis also will be de-identified. Consent forms and payment forms will be stored in a locked file cabinet separate from data in an office that is locked when not occupied.

## **6.3 Data and Safety Monitoring**

### **A. Periodic Data Evaluation**

We conduct relevant interim data analyses at 1/3 (n=20), and 2/3 (n=40) of the way through data collection to examine differences between groups with respect to serious adverse events. If there is a significant difference in number of adverse events between groups, we will halt data collection and consult with the IRB.

### **B. Type of Data Evaluated**

We will track reported adverse events using the Adverse Events Tracking log and categorize such events as mild, moderate and severe and take appropriate action accordingly, as determined by IRB guidelines for reporting. AEs and outcomes will be tracked using the Adverse Events Specifics log.

### **C. Collection of Safety Information**

Participants will be queried regarding their experience of nicotine replacement at the follow-up session. Participants who report adverse events will be counseled on discontinuation.

### **D. Frequency Of Data Collection**

We will collect data at baseline and at study follow-up.

### **E. Reviewer of Data**

Data will be reviewed by the study coordinators, [name] and [name], weekly, and by Drs. [name] and [name] monthly.

### **F. Schedule Of Review Of Cumulative Data**

Protocol version: 03.15.2019

PI Name: [name].

Protocol Title: Addressing Tobacco Among  
Public Housing Residents

17

RESERVED FOR IRB STAMP

DO NOT MODIFY THIS SPACE

  
RUTGERS | eIRB  
APPROVED

IRB ID: Pro20170000679

IRB Form Version: y120116

3/25/2019

Expiration Date:

3/24/2020

Quality assurance of data will be assessed weekly by the study coordinators, [name] and [name]. They will alert to PIs to any discrepancies or observations that suggest risk of appropriate data management procedures.

**G. Tests for Safety Data**

Analysis of variance will be conducted to determine if there are statistically significant differences between the three groups with regards to serious adverse events.

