### **1.5 Sample Size Justification**

We have a target N of 60 smokers (n=20/treatment condition). In terms of race/ethnicity, we anticipate our sample will be reflective of cigarette smokers living in the greater New Brunswick, NJ area: We expect to enroll two participants weekly in order to meet our target N. Estimating that 50% of the sample will make quit attempt during the course of the study, our main outcome of interest, this is adequate to group differences with 95% confidence (CI: 0.38, 0.61).

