### **4.3 Subject Randomization**

We will use a block randomization procedure to allocate participants to one of three groups. Block randomization is a procedure in which participants are randomly allocated to interventions groups within blocks such that an equal number are assigned to each intervention. We will use the Sealed Envelope Ltd. 2017 application to

electronically develop a list of 60 allocation outcomes using a block randomization procedure with 3 intervention groups and block sizes of 3, 6, and 9. A research assistant will use this list to create envelopes for therapists to open (revealing allocation to intervention) after each participant provides informed consent and is deemed eligible to participate in the study.

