**H. Suspension of Research**

If we found significant differences between groups with regards to serious adverse events, we would consult with the IRB to discuss suspending the research.

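### A significant ANOVA on serious adverse events is the stated trigger for halting or IRB consultation, but at n=20 and n=40 no significance test is sensitive enough for that role

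*Protocol*

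**What the plan says.** Protocol 6.3A sets two safety looks: "We conduct relevant interim data analyses at 1/3 (n=20), and 2/3 (n=40) of the way through data collection", in order "to examine differences between groups with respect to serious adverse events". The test is named in 6.3G: "Analysis of variance will be conducted to determine if there are statistically significant differences between the three groups with regards to serious adverse events".

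The consequence of significance appears twice, in different terms. Section 6.3A says: "If there is a significant difference in number of adverse events between groups, we will halt data collection and consult with the IRB". Section 6.3H covers a significant difference in serious adverse events, and there "we would consult with the IRB to discuss suspending the research".

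No section gives an alpha for this test, an expected serious event rate, the handling of a look with no events, or whether the variable is a yes/no indicator or a count per participant. The SAP contains no safety analysis. Its opening paragraph assigns chi-square to dichotomous outcomes and ANOVA or ANCOVA to continuous ones.

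**The concern.** Serious adverse events should be few here: Protocol 4.9A describes the risks as minimal. With about 7 people per arm at the first look and 13 or 14 at the second, an indicator of whether a participant had such an event will be nearly all zeros. An F test assumes roughly normal data with equal variances, and these data are neither. The choice also departs from the SAP's own practice for dichotomous outcomes.

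The larger issue is the use made of the p-value. If by-arm attention to serious events waits for significance, a real excess in one arm will usually pass both looks without an alert, and a non-significant result may be read as reassurance that the data cannot give.

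**Working it through.** **Inputs from the documents.** Protocol 1.5: "We have a target N of 60 smokers (n=20/treatment condition"). Protocol 4.3: "block randomization procedure with 3 intervention groups and block sizes of 3, 6, and 9". The look sizes reproduce: 60/3 = 20 and 2 × 60/3 = 40.

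**Assumptions.** Alpha is 0.05 at each look, unadjusted. The variable is at least one serious event per participant, yes or no. Arm splits are 7/7/6 and 14/13/13. Event rates are varied.

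**Single tables.** Let x be the events and n the size of each arm, X the total events and N the total participants. For 0/1 data, SSB = Σx²/n − X²/N, SST = X − X²/N, SSW = SST − SSB and F = (SSB/2)/(SSW/(N−3)).

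- *3/7, 0/7, 0/6.* SSB = 9/7 − 9/20 = 0.836, SSW = 2.55 − 0.836 = 1.714, F = 0.418/0.1008 = 4.14, p = 0.034. The exact (Fisher-Freeman-Halton) p sums the tables no more likely than this one: (35 + 35 + 20)/1140 = 0.079.
- *3/14, 0/13, 0/13.* SSB = 9/14 − 9/40 = 0.418, SSW = 2.775 − 0.418 = 2.357, F = 0.209/0.0637 = 3.28, p = 0.049. Exact p = (364 + 286 + 286)/9880 = 0.095.
- *All three events in the 6-person arm of 7/7/6.* ANOVA p = 0.011. Exact p = 20/1140 = 0.018. Here both tests are significant.

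**False alerts with equal rates.** Every three-arm table was weighted by its binomial probability. ANOVA is significant with these probabilities:

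| Rate in all arms | n=20 | n=40 |
|---|---|---|
| 2% | 0.05% | 0.4% |
| 10% | 1.9% | 4.4% |
| 20% | 4.2% | 4.97% |

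**Flags when one arm truly differs** (same enumeration):

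| Rates | Look, size of affected arm | ANOVA | Exact |
|---|---|---|---|
| 10%, 1%, 1% | n=20, 7 | 2.3% | 0.3% |
| 10%, 1%, 1% | n=20, 6 | 1.4% | 1.4% |
| 10%, 1%, 1% | n=40, 14 | 12.4% | 3.6% |
| 20%, 1%, 1% | n=20, 7 | 13% | 3% |
| 20%, 1%, 1% | n=20, 6 | 9% | 9% |
| 20%, 1%, 1% | n=40, 14 | 45% | 26% |

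**Why so low.** At a 10% rate the affected arm expects 0.7 events among 7 people and 1.4 among 14. ANOVA needs about three events in that arm with none elsewhere. The chance of three or more among 7 is 1 − 0.9⁷ − 7(0.1)(0.9⁶) − 21(0.01)(0.9⁵) = 1 − 0.478 − 0.372 − 0.124 = 2.6%. The limit comes from the number of people and the rarity of events, not from the choice of F test.

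**What a clean look excludes.** With no events in an arm, the exact two-sided 95% upper limit is 1 − 0.025^(1/n): 41% for n=7 and 23% for n=14.

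**The case against.** The strongest reply is that ANOVA does no demonstrable harm here and that an exact test would detect less. Most of that stands.

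- *A reader might infer that ANOVA raises too many false alarms.* It does not, at these rates. Its false-alert rate is below 5% per look up to a 20% common rate. Over both looks, simulation puts it at 0.4% for a 2% rate and 5.6% for a 10% rate. Its disagreement with the exact test on a 3-0-0 split mainly reflects the exact test's conservatism and depends on which arm has the events.
- *A reader might infer that an undefined F statistic is a serious failure.* F is 0/0 only when nobody has an event (0.98²⁰ = 67% of looks at n=20 under an assumed 2% rate, 0.90²⁰ = 12% under 10%). No test would then flag anything, so no decision changes.
- *A reader might infer that an exact test cures the low sensitivity.* It lowers it, from 12.4% to 3.6% at n=40 in the 10% scenario.
- *A reader might infer that serious events go unseen unless p is below 0.05.* Protocol 6.3B provides for tracking and grading of events with action under IRB guidelines, and 6.3E for weekly and monthly data review. Significance is one route among several.

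The reply does not dispose of the by-arm question. Sections 6.3B and 6.3E describe general tracking and review and promise no comparison between arms. The only between-arm comparison of serious events in the plan is the significance test.

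The yes/no variable is also an assumption. If ANOVA were applied to counts of all adverse events, which the trigger wording in 6.3A allows, these figures would not apply.

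**Conclusion.** The point holds as one about the safety trigger. ANOVA is a poor match for sparse yes/no events and inconsistent with the SAP's rule for dichotomous outcomes, but the calculations do not show it to be misleading in error rate. The material weakness is that the between-arm comparison of serious events rests on a significance test that, at these sizes, misses an assumed 10% v 1% v 1% excess about 98% of the time at n=20 and 88% at n=40. Even at 20% v 1% v 1% it misses about 87% and 55%. These figures assume alpha 0.05 per look, a yes/no variable, near-equal arms and event rates that the documents do not state.

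Separately, 6.3A (number of adverse events, halt) and 6.3H (serious adverse events, consult) differ in both the event and the action, and must be reconciled. No efficacy result is affected.

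**What to change.** 1. In 6.3A and 6.3G, state that at each look the number of participants with at least one serious adverse event is tabulated by arm with exact 95% intervals and a by-arm listing, and is reviewed whatever the p-value of any test. Review then does not wait for significance.
2. If a test is kept, call it supplementary, state its alpha and define the variable. Use a method suited to a yes/no event, such as Fisher-Freeman-Halton, and say that no test is run when there are no events. State openly that this test is materially less sensitive than ANOVA at n=40. It should not be substituted alone as the trigger.
3. Reconcile 6.3A and 6.3H on which events count and what action follows. That choice belongs to the investigators and the IRB.

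The cost is a few sentences and one small table per look, with no effect on sample size or the efficacy analysis. Protocol 1.3 keeps the follow-up research assistant blind to condition, so someone else should prepare the by-arm table. The planned by-arm test already needs such a person. If the looks have already taken place, as the SAP's count of five participants lost to follow-up may suggest, the same table belongs in the final safety report.

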**H. Suspension of Research**

If we found significant differences between groups with regards to serious adverse events, we would consult with the IRB to discuss suspending the research.

**6.4 Reporting Results**

**A. Sharing of Results with Subjects**

N/A

**B. Individual Results**

N/A

**C. Aggregate Results**

Participants will be told that published aggregate study results will be available to them upon their request by contacting the laboratory.

**D. Professional Reporting**

Data from our research will be presented at annual professional organization conferences (e.g., Society for Research on Nicotine and Tobacco) and published in peer-reviewed journals.

**E. ClinicalTrials.Gov Registration And Data Reporting**

We will register the trial with ClinicalTrials.gov

**7.0 Data and/or Specimen Banking**

N/A

**8.0 Other Approvals/Authorizations**

N/A

Official Title: Addressing Tobacco in Public Housing Residents

Identifiers: NCT03620708

Document Date: September 27, 2019

Statistical Analysis Plan

To assess for differences in outcomes between groups we will use chi-square for dichotomous outcomes and analysis of variance / analysis of covariance for continuous outcomes. We will consider covariates based on theoretical grounds (e.g., baseline cigarettes per day, baseline motivation to quit, financial disadvantage) and significant differences between groups at baseline. Significant results will be probed using Dunnett's method, whereby our comparison of interest was between the treatment conditions and control condition. We will further report effect size estimates (i.e., f for ANOVA; Cramer's V for chi-square) to help elucidate aspects of the pilot study that may be most beneficial. Data will also be examined based on the assumption of 'missing equals smoking' and carrying the last observation (i.e., baseline data) forward, as a relatively conservative means of handling data for the n=5 participants lost to follow-up. We will refer to additional analyses of imputed data as intent-to-treat (ITT) analyses.

Outcome 1: A self-described "serious" attempt to quit smoking cigarettes since the initial study appointment, measured by the "Quitting Preparation and Actions Questionnaire."

We will use chi-square analysis to examine differences in proportion of the participants randomized to receive the three intervention groups with respect to making a serious quit attempt between the initial appointment and the 1-month follow-up period.

Outcome 2: Self-reported contact with one of two treatment referrals provided at intervention since the time of the initial study appointment

We will use chi-square analysis to examine differences in proportion of the participants randomized to receive the three intervention groups with respect to seeking treatment at either the NJ QuitLine or a NJ Quitcenter (local tobacco dependence treatment clinic) between the initial appointment and the 1-month follow-up period.

Outcome 3: Self-reported cigarettes smoked per day

We will use Analysis of Covariance (ANCOVA) to examine differences in cigarettes smoked per day at the 1-month follow-up between participants randomized to the three intervention groups. Baseline cigarettes smoked per day and measures of motivation to quit will be included as covariates.

Outcome 4: Motivation and Self-efficacy for quitting smoking measured via Importance, Confidence, & Readiness Questionnaire" (rated on a 0 to 10 scale)

We will use separate Analysis of Covariance (ANCOVA) to examine differences in a) Self-reported Importance of quitting, b) Self-reported Confidence in one's ability to quit, and c) Self-reported Readiness to quit at the 1-month follow-up between participants randomized to the three intervention groups. Baseline ratings of motivation to quit will be included as a covariates.

Outcome 5: "Readiness to Quit Ladder" (with 10 non-numbered choices reflecting varying degrees of readiness

We will use Analysis of Covariance (ANCOVA) to examine differences in cigarettes smoked per day at the 1-month follow-up between participants randomized to the three intervention groups. Baseline score on the Readiness to Quit Ladder will be included as a covariate.

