#### B. Hypotheses / Research Question(s)

Brief advice to quit (i.e., referral), brief motivational interviewing, and nicotine replacement therapy are recommended approaches to promote smoking cessation and reduce health disparities in low-income smokers (Fiore et al., 2008). However, as compared to referring participants to the NJ Quitline, we expect brief MI and provision of NRT to be superior in terms of: (1) Increasing motivation to quit; (2) increasing self-efficacy to quit; (3) setting a quit date; (4) making a cessation attempt; (5) and achieving initial abstinence.

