**6.0 Research Data Protection and Reporting**

**6.1 Data Management and Confidentiality**

**A.** Success of randomization will be checked via summary statistics of baseline demographic and psychosocial characteristics. Depending on the measurement scale of each variable, we will use either  $\chi^2$  or independent samples t-tests, corrected for unequal variances if indicated. Variables found to show significant baseline differences between groups will be included as covariates. Logistic regression analyses will be conducted to examine differences in dichotomous outcomes such as abstinence (yes/no), quit attempts (yes/no), and treatment seeking (yes/no). Because this is a small, pilot study, we will report effect sizes representing each of the two active interventions (MI and NRT sampling) as compared to the control intervention (referral only).

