**B. Provide a power analysis. (As applicable, e.g. quantitative research).**

N/A. This is a small, pilot study. We will use the data collected in this study to estimate effect sizes for a larger NIH grant application.

**C. Describe the steps that will be taken to secure the data (e.g., training, authorization of access, password protection, encryption, physical controls, certificates of confidentiality, and separation of identifiers and data) during storage, use, and transmission.** The link between participants to their study ID will be stored in a password-protected file, located within a password-protected database on an encrypted computer. Only select trained laboratory personnel will have access to the file. All computer files or printed data used for analysis also

will be de-identified. Consent forms and payment forms will be stored in a locked file cabinet separate from data in an office (of Division of Addiction Psychiatry, [name]) that is locked when not occupied. All research personnel will complete CITI Human Subjects Research training and pass the CITI quizzes.

Additionally, we will obtain a Certificate of Confidentiality from the NIH

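### The SAP names only three-group, unsigned effect sizes and makes arm-versus-control comparisons depend on significance, whereas the protocol promises an effect size for each active arm against referral only, without that condition

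*SAP*

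**What the plan says.** Protocol section 6.1 A states that, because the study is a small pilot, "we will report effect sizes representing each of the two active interventions (MI and NRT sampling) as compared to the control intervention (referral only". No significance condition is attached. The same section plans regression for the binary outcomes: "Logistic regression analyses will be conducted to examine differences in dichotomous outcomes such as abstinence (yes/no), quit attempts (yes/no". Section 6.1 B gives no power analysis and states the purpose: "We will use the data collected in this study to estimate effect sizes for a larger NIH grant application". The hypotheses in section 1.1 B are directional and set each active arm against referral: "as compared to referring participants to the NJ Quitline, we expect brief MI and provision of NRT to be superior in terms of".

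The SAP is the later document. For Outcomes 1 and 2 it plans a three-group test ("We will use chi-square analysis to examine differences in proportion of the participants randomized to receive the three intervention groups"), and for Outcomes 3 to 5 a three-group ANCOVA. Its general paragraph then says: "Significant results will be probed using Dunnett's method, whereby our comparison of interest was between the treatment conditions and control condition". On effect sizes it says: "We will further report effect size estimates (i.e., f for ANOVA; Cramer's V for chi-square". No risk difference, odds ratio, mean difference or interval for either active arm against control is named anywhere in the SAP.

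**The concern.** Cramer's V and Cohen's f measure how far three groups differ from one another. Neither carries a sign, and neither says which arm is responsible. They therefore cannot show whether MI or NRT did better than referral, which is what the hypotheses ask. Nor do they give the planner of a larger trial a difference to build on.

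The comparison that would do this, each treatment against control, is planned only as a follow-up to a significant result. With about 20 participants per arm that step may often not be reached when effects are modest. If arm-level contrasts were presented only when it is reached, those presented would be a selected set and too large on average. The pilot's stated product would then be either absent or biased upward.

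**Working it through.** **Inputs.** From protocol section 1.5: 60 participants, 20 per arm, and an expected overall quit-attempt rate of 50% ("Estimating that 50% of the sample will make quit attempt during the course of the study, our main outcome of interest"). From the SAP: 5 lost to follow-up. Assumed, because the documents do not state them: alpha 0.05 for the three-group test, and the arm-specific true rates below.

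**The plan's own figure.** The documents give no effect size or power to reproduce. The one precision figure, 0.38 to 0.61 in section 1.5, concerns a single overall proportion. A Wilson interval for 30/60 gives 0.377 to 0.623, so the stated interval does not reproduce exactly. Nothing below depends on it.

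**Step 1: does V show direction or arm?** Chi-square = sum of (observed - expected)² / [n p(1 - p)], with n = 20 per arm and p the pooled rate; V = sqrt(chi-square/60). Counts are MI/NRT/control.

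- 14/10/10: p = 34/60 = 0.567, expected 11.33 per arm, squared deviations 7.11 + 1.78 + 1.78 = 10.67, divisor 20 × 0.567 × 0.433 = 4.911. Chi-square = 2.172, p-value 0.338, V = sqrt(2.172/60) = 0.190.
- 6/10/10: p = 26/60 = 0.433, expected 8.67 per arm, the same squared deviations and the same divisor. Chi-square = 2.172, p-value 0.338, V = 0.190.

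The MI-control differences are 14/20 - 10/20 = +0.20 (Newcombe 95% CI -0.10 to 0.45) and 6/20 - 10/20 = -0.20 (-0.45 to 0.10). One points with the hypothesis and the other against it, yet the planned summary is identical.

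V does not identify the arm either. Counts of 14/8/8 and 8/14/8 both give chi-square 4.80, p = 0.091, V = 0.283. In the first the 0.30 excess over control is in MI, and in the second it is in NRT.

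**Step 2: how often would the per-arm step be reached?** Exact enumeration of all 21³ tables with 20 per arm, counting a table as significant when chi-square exceeds 5.991 (2 df). The assumed rates average the protocol's 50%.

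| True MI/NRT/control | Step reached | True MI-control difference | Mean difference when reached |
|---|---|---|---|
| 60/50/40% | 18.5% | 0.20 | 0.39 |
| 65/50/35% | 38% | 0.30 | 0.44 |
| 70/50/30% | 63% | 0.40 | 0.48 |
| 75/50/25% | 85% | 0.50 | 0.54 |

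The overstatement is 0.19, 0.14, 0.08 and 0.04 in turn, so it shrinks as the true effect grows.

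**Step 3: sensitivity.** With 55 followed up (60 less 5, split 18/18/19 in any order), the step is reached in 17.5-19%, 35-38%, 58-62% and 80-84% of trials. With 20 per arm and both active arms at 60% against a control at 30%, it is reached in 49%, and a true difference of 0.30 averages 0.40.

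**The case against.** The SAP does not withdraw the protocol's commitment. Its effect-size sentence adds to the tests and carries no significance condition, and it names treatment versus control as the comparison of interest. That f and V are the whole list is an inference from the wording of a very short document. The inference is reasonable, but the SAP nowhere says that it drops the protocol's effect sizes. This stands, and it makes the point one of reconciliation.

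Arm counts may well be reported. If they are, a reader can rebuild a crude risk difference or odds ratio for the binary outcomes, and the sign ambiguity in Step 1 disappears. This also stands. It does not help the continuous outcomes, because ANCOVA-adjusted differences cannot be recovered from raw means.

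The selection effect in Step 2 arises only if arm-level contrasts are withheld when the three-group test is not significant, and the SAP does not say that they will be. The MI > NRT > control ordering is illustrative; no document suggests it.

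Two stronger readings are tempting and are not supported. A reader might infer that the significance condition hides effects that the SAP's own method would declare. With NRT and control at 10/20 and MI at 16/20, the three-group p is 0.08, while an unadjusted Newcombe interval for MI minus control is 0.005 to 0.53. But the SAP's comparison is Dunnett's. At its two-sided critical value of 2.268 (two comparisons, 57 df), the interval becomes -0.04 to 0.56 and includes zero. At 17/20 the three-group p is 0.03 and the adjusted interval, 0.01 to 0.60, excludes zero. In this pattern the two procedures agree. A reader might also infer that the SAP drops promised confidence intervals. The protocol promises effect sizes per arm and does not mention intervals for them.

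**Conclusion.** The mismatch is real. The protocol promises an effect size for each active arm against referral only, without condition. The SAP names only three-group, unsigned measures and plans the per-arm comparison for significant results only. The tests themselves remain valid; what the analysis plan lacks is the quantity that the pilot says it exists to estimate.

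That V cannot show sign or arm is arithmetic and rests on no assumed rates. The 18.5% to 85% range rests on alpha 0.05, 20 per arm and the illustrative rates. The overstatement (0.39 against 0.20, narrowing to 0.54 against 0.50) also requires that contrasts are shown only after a significant three-group test. The practical loss is greatest for the adjusted continuous outcomes, which cannot be rebuilt from arm summaries. This should be corrected, and confidence in it is high.

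**What to change.** Reconcile the SAP with protocol section 6.1. For every outcome, and whatever the three-group p-value, report a signed estimate for MI versus control and for NRT sampling versus control: a risk difference or odds ratio for binary outcomes, and the ANCOVA-adjusted mean difference for continuous outcomes. V and f may stay as supplements.

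As a recommended addition beyond what the protocol promises, give each estimate a 95% confidence interval under one stated multiplicity convention for all outcomes, either all unadjusted or all Dunnett-type.

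The cost is a sentence or two and slightly more output, with no new data. Intervals will be wide: unadjusted, about 1.96 × sqrt(2 × 0.25/20) = ±0.31 on a risk difference near 50%. That width is itself something the planner of a larger trial needs to see.

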**Visit 1:** Following the initial phone screen study staff will arrange to meet with eligible participants to administer additional measures as well as the brief intervention. In addition to verifying inclusion/exclusion criteria as well as smoking status, participants will be asked to complete a questionnaire battery online using a laptop provided by study staff, and a brief interview to further assess motivation and confidence to quit, substance use, physical health, and mental health status and history, as well as smoking cessation history.

**Study Interventions:** Next, we will use a block randomization procedure to allocate participants to one of three groups: A *single session motivational intervention (MI)*, which will include a 30-minute therapy session designed to enhance motivation to quit smoking, followed by a referral to the NJ State Quitline and local Tobacco Dependence Program; (2) An *NRT sample intervention*, which will include free two-week supplies of nicotine patches and nicotine lozenge with instructions for proper use and a referral to the NJ State Quitline and local Tobacco Dependence Program, or (3) An *assessment and referral only control*.

Block randomization is a procedure in which participants are randomly allocated to intervention groups within blocks such that an equal number are assigned to each intervention. We will use the Sealed Envelope Ltd. 2017 application to electronically develop a list of 60 allocation outcomes using a block randomization procedure with 3 intervention groups and block sizes of 3, 6, and 9. The study coordinator will use this list to inform study therapists of the intervention to which participants were assigned.

Upon completion of the intervention, participants will be scheduled for a one-month follow-up visit with a research assistant. Participants will be reminded of their appointment via text, phone, and email 48 and 24 hours prior.

**One-month Follow-up:** Participants will be asked to complete a brief online survey once again, and smoking status will be verified via self-report and carbon monoxide analysis of breath sample. Staff will also conduct brief interviews to assess main outcomes of interest.

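### The SAP's omnibus f and Cramer's V, reported without bias correction or interval across seven tests, are likely to let chance be read as benefit

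*SAP*

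**What the plan says.** The general paragraph of the SAP plans chi-square tests for dichotomous outcomes and ANOVA or ANCOVA for continuous ones. It then adds: "We will further report effect size estimates (i.e., f for ANOVA; Cramer's V for chi-square"). The stated purpose is "to help elucidate aspects of the pilot study that may be most beneficial". Dunnett comparisons with control follow only a significant overall result; the effect sizes are not conditional on significance.

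The SAP lists five outcomes, which give seven three-group tests: one each for Outcomes 1, 2, 3 and 5, and three for Outcome 4 ("We will use separate Analysis of Covariance (ANCOVA) to examine differences in a) Self-reported Importance of quitting", then confidence and readiness). The data are examined a second time with imputation: "We will refer to additional analyses of imputed data as intent-to-treat (ITT) analyses".

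Three protocol statements bear on this:
- Section 1.5 identifies quit attempt as the main outcome: "Estimating that 50% of the sample will make quit attempt during the course of the study, our main outcome of interest". The SAP lists it first but gives it no special status.
- Section 6.1 A promises effect sizes for MI and for NRT sampling, each against referral only.
- Section 6.1 B declines a power analysis and says the data will be used to estimate effect sizes for a larger grant application.

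**The concern.** Effect sizes are the main product of this pilot, so their behaviour in a sample of this size matters more than the p-values. Two properties of the chosen statistics are a problem.

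First, f and V cannot fall below zero. Sampling error therefore always pushes them up, and with about 18 participants per arm they lie well above zero when no arm does anything.

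Second, they are omnibus. A given f or V could mean that MI helped, that NRT sampling helped, or that an active arm did worse than control. They cannot show which intervention was beneficial, although that is what the SAP wants to learn.

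Seven such numbers side by side, with no main outcome and no intervals, invite the reader to look for the largest. A chance value could then shape the target or the assumed effect of the next trial.

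**Working it through.** **Inputs**
- Three arms ("we will use a block randomization procedure to allocate participants to one of three groups"), so each test has 2 numerator degrees of freedom.
- Size: "We have a target N of 60 smokers (n=20/treatment condition").
- Loss: "handling data for the n=5 participants lost to follow-up", so 60 − 5 = 55 analysed. This assumes 60 were randomised; Protocol 4.5 also gives a total of 64.
- One covariate per ANCOVA (assumed), so the error df are 55 − 3 − 1 = 51.
- For simulation: arms of 18, 18 and 19; binary rates of 50% (Protocol 1.5) and 30% (assumed); equal correlation between outcomes.

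The documents give no expected or null value of f or V, so there is no figure of the plan's own to reproduce here.

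**One test, no true effect**

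For a 3×2 table V = √(χ²/N), with χ² on 2 df:
- mean V = √(π/2)/√55 = 1.253/7.416 = 0.169
- P(V > 0.25) = exp(−55 × 0.0625/2) = exp(−1.719) = 0.179

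For ANCOVA f = √(2F/51), with F on (2, 51) df, so P(f > x) = (1 + x²)^(−51/2):
- mean f = (√π/2) × Γ(25)/Γ(25.5) = 0.178
- median f = √(2^(2/51) − 1) = 0.166
- P(f > 0.25) = 1.0625^(−25.5) = 0.213

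The value 0.25 is only a reference point; neither document uses it. If instead 64 were randomised and 59 analysed, mean V = 1.253/√59 = 0.163 and P(f > 0.25) = 1.0625^(−27.5) = 0.189.

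**Largest of seven (two V, five f), no true effect**

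For independent outcomes, P(largest > 0.25) = 1 − (1 − 0.179)² × (1 − 0.213)⁵ = 1 − 0.674 × 0.302 ≈ 0.80. Simulation gives 79% and extends this to correlated outcomes:

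| Correlation | Mean of largest | Share above 0.25 |
|---|---|---|
| 0 | 0.31 | 79% |
| 0.5 | 0.30 | 68% |
| 0.8 | 0.27 | 53% |

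**Contribution of the imputed data**

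Taking the largest over both data sets moves its mean only from 0.316 to 0.320 (independent outcomes). The two sets share 55 of 60 participants, and their effect sizes correlate 0.90 to 0.97.

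**When something does work**

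If one continuous outcome has a true f of 0.25 and the other six outcomes have no effect, the true one ranks first in only about 50% of trials.

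**What correction and intervals do**
- Adjusted f = √max(0, 2(F − 1)/N): null mean about 0.07, exactly zero in 63% of trials.
- Bias-corrected V, which subtracts 2/(N − 1) = 2/54 = 0.037 from V² and truncates at zero before rescaling: null mean about 0.06, zero in 64%.
- A 95% noncentral-F interval for an observed f of 0.25 runs from 0 to 0.48. At the null median of 0.166 it runs from 0 to 0.39.
- The largest of seven corrected effects still averages 0.16 to 0.23 under the null and exceeds 0.25 in 25% to 41% of trials (correlation 0.8 to 0). Correction removes most of the bias in a single estimate but not the effect of selection.

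**The case against.** The strongest defence is that the SAP contains no selection rule. Its wording is tentative, and it sets no threshold and no ranking. A reader might infer that the plan will pick the largest f or V and so will select noise. The documents do not support that: noise is certain to be picked only if someone ranks the outcomes and nothing works. The largest-of-seven figures describe what happens if outcomes are compared by size, not a procedure the SAP prescribes. This part of the defence stands.

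A reader might also infer that the second, imputed analysis doubles the problem. It does not. It is a labelled sensitivity analysis for five participants and adds almost nothing.

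Nor do the documents say that the largest f or V goes into the grant application. Protocol 6.1 B refers to effect sizes generally, and those described in 6.1 A are arm-versus-control. But the SAP names only omnibus ones, so it does not deliver what 6.1 A promised.

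Three smaller points are fair. The absence of bias correction is inferred from the SAP's silence. The protocol does name a main outcome and does call this a small pilot without a power analysis. The analysis text of Outcome 5 names cigarettes per day although its heading is the Readiness to Quit Ladder, so it is not certain that readiness is tested twice; the count of seven tests is unchanged.

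Pilot status does not answer the point, because effect estimation is this pilot's declared purpose.

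**Conclusion.** The concern holds in a limited form. As written, the SAP will produce effect sizes that are biased upward and have no direction or stated uncertainty, for a use that needs all three put right. The single-test figures depend on 55 analysed and hardly move at 59. The largest-of-seven figures are conditional: they assume no effect on any outcome, equal correlation between 0 and 0.8, and a reader who compares outcomes by size. Four of the seven outcomes are, by their headings, ratings of motivation, confidence or readiness, so the higher correlations are plausible and the lower end of the range should be kept in view. Even there, chance alone gives a largest value above 0.25 in about half of trials. The causes are the small sample and the number of outcomes. The SAP should be changed, but nothing in it shows that a false finding will necessarily be carried forward.

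**What to change.** 1. For each outcome, report MI against control and NRT sampling against control, as a risk difference or an adjusted mean difference, each with a 95% CI. This restores the commitment in Protocol 6.1 A and gives direction.
2. If f and V are kept, use the omega-squared-based f and the bias-corrected V, with 95% CIs.
3. Carry the main outcome of Protocol 1.5 (quit attempt, SAP Outcome 1) into the SAP as the basis of the conclusion, in one named analysis set. Label all other outcomes descriptive.
4. State that aspects of the pilot will not be compared by effect size across outcomes. Step 2 alone does not achieve this.

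The cost is SAP wording and a different formula, with no new data. Reported effect sizes will be smaller and visibly imprecise. For example, at 50% quit attempts and 20 per arm the risk difference has a 95% half-width of 1.96 × √(2 × 0.25/20) = 0.31. A later grant application should show that imprecision.
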